14.3 Secondary Efficacy Endpoints

The primary analyses for the secondary endpoints will be performed on the 110 subjects in the mITT population who will be followed up for approximately 6 months in the non-interventional study 270-902 prior to their enrollment in 270-301. The baseline values will be derived from the prospectively collected data in 270-902.

For the first secondary efficacy endpoint at Week 52 (ie, the change in the annualized utilization (IU/kg) of exogenous FVIII replacement therapy during Weeks 5-52 post-BMN 270 infusion from baseline), a one-sample t-test will be performed to test the null hypothesis that the change is 0 or greater against the alternative hypothesis that the change is less than 0. The missing value of the change will be imputed as 0.

For the second secondary efficacy endpoint at Week 52 (ie, the change in ABR, annualized bleeding rate, during Weeks 5-52 post-BMN 270 infusion from baseline), a one-sample t-test will be performed to test for non-inferiority of BMN 270 against FVIII prophylaxis (ie, the baseline ABR calculated using subjects' data collected as part of 270-902) using a non-inferiority margin of 3.5, ie, to test the null hypothesis that the change is 3.5 or greater against the alternative hypothesis that the change is less than 3.5. If non-inferiority is demonstrated, the test for superiority of BMN 270 against FVIII prophylaxis will be performed. The missing value of the change will be imputed using the median value of the changes of all observed cases.

A sensitivity analysis is planned to analyze ABR using a generalized linear mixed model assuming negative binomial as the underlying distribution. The model will include period (pre- to post-BMN 270 infusion) as the only factor. The actual number of bleeding episodes

Page 113

will be used as the independent variable with the time period adjustment (animalization) being implemented as the offset.

To assess the impact of missing data, analyses using observed case are planned as sensitivity analyses for the secondary endpoints. Multiple imputation methods may also be performed.

The primary and secondary efficacy hypotheses will be tested hierarchically according to the order described above. Multiple comparison procedures will be described in greater detail in the SAP.

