For the analytic sample size calculation of the second secondary endpoint, ABR, it is assumed that the pre- and post-BMN 270 infusion population mean ABRs are 3.5 and 1 respectively, and the distribution of ABRs is negative binomial distribution with a dispersion parameter of 2.2. Given the underlying negative binomial distributions, the standard deviations of the pre- and post-BMN 270 infusion ABRs are calculated as 7.8 and 1.8 respectively. The mean (SD) of the change from the pre- to post-BMN 270 infusion ABRs are calculated as -2.5 (8) assuming the correlation between pre- and post-BMN 270 infusion ABRs is zero. Under this assumption, an analytic sample size of 110 will also have at least 95% power to demonstrate that the change in the annualized number of bleeding episodes requiring exogenous FVIII replacement treatment (ABR) during Week 5 to Week 52 of the study post-BMN 270 infusion from the baseline ABR is less than 3.5 (non-inferiority margin), using a one-sample t-test with a 2-sided significance level of 0.05. Under the same assumptions, a sample size of 110 will have approximately 90% power to

Page 115

demonstrate that the change is less than 0, ie, superiority of BMN 270 against FVIII prophylaxis.

Overall, the planned sample size will have greater than 80% power for testing the primary and secondary efficacy endpoints hierarchically at the final analysis with a 2-sided significance level of 0.05.

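### Filling missing ABR changes with the observed median, then running an ordinary t-test on all 110 subjects, makes the standard error too small by about the missing fraction and weakens error control at the non-inferiority margin

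*Protocol*

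**What the plan says.** Section 14.3 (Amendment 3) sets the primary analysis of the change in annualised bleeding rate (ABR). The analysis set is fixed: "The primary analyses for the secondary endpoints will be performed on the 110 subjects in the mITT population", namely those followed in study 270-902 beforehand. The test is a one-sample t-test, "to test the null hypothesis that the change is 3.5 or greater against the alternative hypothesis that the change is less than 3.5", with superiority tested next if non-inferiority is shown. For missing data the rule is: "The missing value of the change will be imputed using the median value of the changes of all observed cases".

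The same section plans observed-case analyses and a negative binomial mixed model with a time offset, both as sensitivity analyses, and says that multiple imputation may be performed. Section 14.1.2 leaves additional missing-data details to the SAP. Section 9.3.4 says that subjects who withdraw after dosing are not replaced. No dropout rate or expected missing fraction is given.

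Section 14.7 supplies the planning model. It takes mean ABRs of 3.5 before and 1 after infusion. On their shape it says: "the distribution of ABRs is negative binomial distribution with a dispersion parameter of 2.2". It derives a change of -2.5 (SD 8) with zero correlation between periods, tested "using a one-sample t-test with a 2-sided significance level of 0.05".

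**The concern.** The rule has two faults that do not depend on each other.

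- **Too little variance.** Every filled-in value is the same constant. It adds almost nothing to the sum of squares but counts fully in n. The t-test therefore reports more precision than the data hold, whatever the distribution.
- **Wrong centre.** The t-test concerns the mean change, while the fill-in is the median. ABR changes built from overdispersed counts are skewed, so the two can be far apart and the estimate shifts.

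Non-inferiority to prophylaxis on bleeding is a confirmatory claim in a single-arm trial, so there is no second arm in which these errors could offset each other. Where the change is right-skewed at the margin, both faults act in the same direction and missing data make the claim easier to win. The sensitivity analyses would reveal this, but they do not govern the test.

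**Working it through.** **Inputs.** From Sections 14.3 and 14.7: n = 110; mean ABR 3.5 before and 1 after infusion; negative binomial with dispersion 2.2; zero correlation; margin 3.5; 2-sided 0.05, so 0.025 in the non-inferiority direction. Assumed, because the protocol gives no figure: 5%, 10% and 15% of changes missing, completely at random.

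**The plan's own figures reproduce.**
- Pre-infusion SD: sqrt(2 × (3.5 + 2.2 × 3.5²)) = 7.80. Post-infusion SD: sqrt(1 + 2.2 × 1²) = 1.79. SD of the change: sqrt(7.8² + 1.8²) = 8.0.
- Standard error: 8/sqrt(110) = 0.763. Superiority: 2.5/0.763 = 3.28, power 90.1%. Non-inferiority: (3.5 + 2.5)/0.763 = 7.87, power above 99.99%.

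**Standard error under the rule.** With m of n values set to a constant near the centre, the ratio to the observed-case standard error is about sqrt[((n-m-1)/(n-1)) × ((n-m)/n)], which is close to 1 - p for missing fraction p. For m = 11: sqrt[(98/109) × (99/110)] = 0.90. The ratio is about 0.95 at 5% missing and 0.85 at 15%.

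**Normal changes, true change 3.5.** The one-sided error is about Φ(-1.96 × (1 - p)), which is 3.1% at 5% and 3.9% at 10%. Simulation gives about 3.2%, 3.9% and 4.7% at 5%, 10% and 15%. The observed-case test stays at 2.4-2.6%.

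**Negative binomial changes, true change 3.5.** Rates of 3.5 before and 7 after, dispersion 2.2, independent periods, 6-month baseline and 48-week follow-up. The mean change is 3.5 but the median is about 0.96. At 10% missing the estimate moves by 0.10 × (0.96 - 3.5) = -0.25 bleeds per year, away from the margin. Simulated one-sided error (nominal 2.5%):

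| Missing | Median rule | Observed cases | Ratio |
|---|---|---|---|
| 0% | 3.9% | 3.9% | 1.0 |
| 5% | 5.4% | about 4.0% | about 1.4 |
| 10% | 7.2% | about 4.1% | about 1.8 |
| 15% | 9.0% | about 4.1% | about 2.2 |

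The 3.9% in the first row comes from t-test skewness, with nothing imputed. With 2 of 110 missing the error is about 4.4%.

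**Sensitivity to the model.** Annualising 6-month counts with dispersion 2.2 gives a pre-infusion SD of 2 × sqrt(1.75 + 2.2 × 1.75²) = 5.8, not the stated 7.8. Forcing the SD to 7.8 gives 3.1% with complete data, 4.1% at 5% and 5.1% at 10%. If the left-skewed planning distribution is simply shifted so that its mean is 3.5, the error is below nominal and falls further with imputation (1.1% complete, 0.7% at 10%).

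**At the planned effect (-2.5).** The median change is about -0.3, so at 10% missing the estimate moves by 0.10 × (-0.3 + 2.5) = +0.22, towards zero. Coverage of the 95% interval is about 94% for observed cases and 91%, 88% and 84% under the rule. Superiority error is not inflated (2.1-2.5%), and non-inferiority power stays near 100%.

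**The case against.** The strongest reply is that few changes may be missing at all. The endpoint is an annualised rate, so a subject with partial Week 5-52 follow-up can still have a value. Visits are weekly to Week 36, and Section 12.8 collects bleeding data at early termination. On that reading only subjects with almost no follow-up after Week 4 are missing, and with one to three of them the inflation is small. This stands as a limit on size. The protocol does not say, however, that partial follow-up counts as observed, and a rule that is harmless only when it is hardly used is still a poor primary rule.

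The planned sensitivity analyses are also a fair point. They would expose a discrepancy, but they do not replace the primary result.

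Three stronger readings are tempting and are not supported.

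- **That the rule inflates error two- to four-fold.** Against the nominal 2.5%, the negative binomial figures of 5.4% to 9.0% are 2.2 to 3.6 times. But 3.9/2.5 = 1.6 of that is present with no missing data, the missing fractions are assumed, and normal changes, an SD of 7.8 or left skew all give less. Larger figures arise if the two periods share a subject effect, but Section 14.7 assumes zero correlation.
- **That the rule contradicts the one for FVIII use,** where "The missing value of the change will be imputed as 0". The endpoints and nulls differ. Zero is the null for FVIII use, but for ABR non-inferiority it lies 3.5 below the margin; filling in zero there gave slightly more error than the median (7.5% against 7.0% at 10% missing).
- **That the rule always favours the product.** At the planned effect it pulls the estimate towards no effect.

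**Conclusion.** The point holds in a conditional form. The understated standard error follows from the rule itself and is about the missing fraction under any distribution. The effect on type I error depends on a missing fraction that the protocol does not give and on the shape of the changes at the margin. Under the protocol's negative binomial assumption with independent periods and data missing completely at random, imputation alone multiplies the one-sided non-inferiority error by about 1.4, 1.8 and 2.2 at 5%, 10% and 15% missing; with normal changes the multipliers are about 1.3, 1.5 and 1.9. The loss of interval coverage at the planned effect is partly bias against the product. The issue is error control and a valid interval, not the expected outcome of the non-inferiority test.

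**What to change.** Delete the median rule in Section 14.3 and carry the replacement into the SAP:

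- Annualise over the time actually observed for every subject with any Week 5-52 follow-up.
- For subjects with none, impute the null value: 3.5 for the non-inferiority test and 0 for superiority.
- Alternatively, make proper multiple imputation from the negative binomial model the primary method.

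In simulation, imputing the margin kept the non-inferiority error at its complete-data level (3.9-4.0%). It does not remove the excess due to skewness.

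The cost is a sentence or two of text and some conservatism for superiority. With the plan's -2.5 (SD 8) and a fraction p imputed as 0, the mean is -2.5(1 - p) and the variance is 64(1 - p) + 6.25p(1 - p). At p = 0.15 that is -2.125 and 55.2, so 2.125/sqrt(55.2/110) = 3.00 and power is about 84%. At 5% and 10% power is about 88% and 87%, against about 90% with complete data. The loss applies only to subjects with no follow-up at all.

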14.4 Immunogenicity

Analysis of total and neutralizing antibody response and other immunological parameters will be primarily descriptive and involve both inter-subject and intra-subject comparisons.

14.5 Pharmacodynamic Analyses

Plasma FVIII protein concentrations and FVIII activities determined over the course of the study will primarily be evaluated and summarized with descriptive statistical measures (eg, mean, standard deviation, CV%, min, median, max).

14.6 Safety Analysis

The Medical Dictionary for Regulatory Activities terminology (MedDRA) will be used by the Sponsor to assign system organ class and preferred term classification to events and diseases, based on the original terms entered on the eCRF.

All AEs will be coded using the current version of MedDRA. The incidence of AEs will be summarized by system organ class, preferred term, relationship to study drug, and severity. A by-subject listing will be provided for those subjects who experience a serious AE (SAE), including death, or experience an AE associated with early withdrawal from the study or study drug.

Clinical laboratory data will be summarized by the type of laboratory test. For each clinical laboratory test, descriptive statistics will be provided on Baseline as well as all subsequent visits. Descriptive statistics for physical examination results and vital signs will also be provided.

Detailed statistical methods will be provided in the SAP.

Page 114

14.7 Determination of Sample Size

Approximately one hundred and thirty (130) subjects may be dosed in the study. The sample size for this study is based on clinical and statistical considerations in order to provide sufficient data to assess both safety and efficacy of BMN 270.

For the primary endpoint, a sample size of 130 will provide at least 95% power to demonstrate that the change in hFVIII activity during Weeks 49-52 from baseline is greater than 0, assuming an effect size of 0.6, using a one-sample t-test with a 2-sided significance level of 0.05. The effect size of 0.6 is assumed based on Study 270-201 data. In Study 270-201 cohort 6E13, the mean (SD) of FVIII activity (IU/dL) at Week 52 (based on median values in a 4-week window around Week 52) were estimated as 103.8 (62.4), with a 95% confidence interval for the mean of (46.1, 161.5). Using the lower limit of the confidence interval and assuming a baseline value of 1 (the largest value allowed per the study's inclusion/exclusion criteria), the effect size of change from baseline is approximately 0.7. For the sample size calculation, an effect size of 0.6 is assumed.

For the secondary endpoints, the analysis will be performed utilizing exogenous FVIII use and bleeding episode data from the 110 subjects whose baseline data will be prospectively collected for approximately 6 months in the non-interventional study 270-902, prior to their enrollment in Study 270-301. An analytic sample size of 110 will provide at least 95% power to demonstrate that the change in the annualized utilization (IU/kg) of exogenous FVIII replacement therapy during Week 5 to Week 52 post-BMN 270 infusion from the baseline is less than 0, assuming an effect size of 0.6 conservatively, using one-sample t-test with a 2-sided significance level of 0.05.

For the analytic sample size calculation of the second secondary endpoint, ABR, it is assumed that the pre- and post-BMN 270 infusion population mean ABRs are 3.5 and 1 respectively, and the distribution of ABRs is negative binomial distribution with a dispersion parameter of 2.2. Given the underlying negative binomial distributions, the standard deviations of the pre- and post-BMN 270 infusion ABRs are calculated as 7.8 and 1.8 respectively. The mean (SD) of the change from the pre- to post-BMN 270 infusion ABRs are calculated as -2.5 (8) assuming the correlation between pre- and post-BMN 270 infusion ABRs is zero. Under this assumption, an analytic sample size of 110 will also have at least 95% power to demonstrate that the change in the annualized number of bleeding episodes requiring exogenous FVIII replacement treatment (ABR) during Week 5 to Week 52 of the study post-BMN 270 infusion from the baseline ABR is less than 3.5 (non-inferiority margin), using a one-sample t-test with a 2-sided significance level of 0.05. Under the same assumptions, a sample size of 110 will have approximately 90% power to

Page 115

demonstrate that the change is less than 0, ie, superiority of BMN 270 against FVIII prophylaxis.

Overall, the planned sample size will have greater than 80% power for testing the primary and secondary efficacy endpoints hierarchically at the final analysis with a 2-sided significance level of 0.05.

14.8 Analysis Populations

The intention-to-treat (ITT) population is defined as all subjects who receive BMN 270 infusion, and the modified intention-to-treat (mITT) population is defined as subjects who receive BMN 270 infusion and are HIV-negative. The mITT population will be used for the primary efficacy analysis and ITT will be used for the supportive efficacy analysis. The ITT population will also be used for the safety analysis.

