In order to minimize bias in the ongoing study and to assure safe and ethical conduct of the clinical trial, an independent Data Monitoring Committee (DMC), consisting of experts in clinical trials, statistics, and hemophilia, has been convened. The DMC will have sole access during the trial to amalgamated FVIII activity levels, FVIII usage, and bleeding data and review available safety and efficacy (eg, FVIII activity) data during the study on an ongoing basis; they may determine, based on emerging data and the risk/benefit profile, that further enrollment at 6E13 vg/kg should be discontinued in favor of a different dose of BMN 270, not to exceed 6E13 vg/kg. If the DMC recommends a dosing modification, then additional subjects may be enrolled, up to a total of approximately 130 subjects, at the new BMN 270 dose level (regardless of the number of subjects previously enrolled at 6E13 vg/kg).

An interim analysis is planned after 20 evaluable HIV-negative subjects have completed the Week 26 visit. Data will be reviewed by the DMC, based on the statistical analysis plan, and a formal recommendation will be made whether to continue the study as designed.

The final analysis for the study will be performed after all subjects have been followed for 52 weeks post-BMN 270 infusion. After the final analysis, safety and efficacy will then continue to be assessed long-term in all subjects for a total of approximately 5 years.

To avoid breakthrough bleeding, subjects will only discontinue exogenous prophylactic FVIII replacement therapy 4 weeks following infusion of BMN 270. Four weeks represents the time by which endogenous production of FVIII following gene transfer is expected to be efficacious, based on earlier results.

Page 13

NAME OF COMPANY	SUMMARY TABLE	FOR NATIONAL
BioMarin Pharmaceutical Inc.	Referring to Part of the	AUTHORITY USE
[name]	Dossier:	ONLY:
[name]		
	Volume:	
NAME OF FINISHED PRODUCT:		
BMN 270	Page:	
NAME OF ACTIVE INCREDIENT.		
NAME OF ACTIVE INGREDIENT:	Reference:	
AAV5-hFVIII-SQ		

In subjects who experience recurring bleeding episodes, the Investigator and Medical Monitor will discuss whether to resume prior FVIII prophylaxis.

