9.4.6 Selection of Dose Used in the Study

Data from an ongoing first in human study (Clinical Study 270-201) indicates that following single escalated doses of BMN 270 (6E12, 2E13, 4E13, 6E13 vg/kg), dose-related increases in FVIII activity were observed, with concurrent improvements in bleeding episodes and

Page 65

exogenous FVIII utilization, particularly at the 4E13 and 6E13 vg/kg dose levels. At all dose levels, BMN 270 is considered to be well-tolerated with mild increases in ALT as the most common adverse event. Please refer to the IB for detailed efficacy and safety data.

In order to further evaluate the dose-response relationship of BMN 270, subjects will be enrolled at a dose of 6E13 vg/kg. This dose is expected to be safe and effective based on clinical experience to date in 270-201. The DMC will review emerging safety and efficacy data and may recommend that a different dose (not to exceed 6E13 vg/kg) be administered. In such a case, up to 130 additional subjects may be enrolled at the new dose.

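### If the DMC changes the dose, section 14.8 as written pools the stopped dose with the dose carried forward in the confirmatory tests

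*Protocol*

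**What the plan says.** All references are to the Protocol, Amendment 3.

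- **Dose switch.** The Synopsis (Study Design and Plan) and section 9.1 allow the DMC to end enrolment at 6E13 vg/kg in favour of a different dose, not above 6E13. Then "additional subjects may be enrolled, up to a total of approximately 130 subjects, at the new BMN 270 dose level", whatever number was enrolled before. Section 9.4.6 puts it as "In such a case, up to 130 additional subjects may be enrolled at the new dose". Sections 9.2 and 15 repeat the DMC's power to recommend this.
- **Populations.** Section 14.8 makes infusion the only condition for the ITT set. For the primary efficacy set it adds HIV status and nothing more: "the modified intention-to-treat (mITT) population is defined as subjects who receive BMN 270 infusion and are HIV-negative". The ITT set serves the supportive and safety analyses.
- **Tests.** Section 14.2 applies one one-sample t-test to the change in FVIII activity. Section 14.3 states that "The primary analyses for the secondary endpoints will be performed on the 110 subjects in the mITT population", meaning those enrolled from study 270-902, again with one-sample t-tests. The ABR hypothesis is non-inferiority of BMN 270, without a dose, at a margin of 3.5.
- **Numbers.** Section 14.7 says "Approximately one hundred and thirty (130) subjects may be dosed in the study". Section 9.4.5 gives about 130 at 6E13.

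**The concern.** A two-dose final data set is a possibility the protocol itself provides for, but the population definitions were written for one dose. Followed literally after a switch, they put every HIV-negative treated subject, at either dose, into a single mean and a single test.

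That mean estimates the effect of neither dose. An effective stopped dose can carry a weaker new dose through the test, and a poor stopped dose can pull down a good new one. Either way, the stated significance level no longer describes the error rate for the dose going forward. If the question is left until a switch happens, the choice between pooling and separating would be made in an open-label trial after emerging data had prompted the switch.

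**Working it through.** **Inputs.** From sections 14.3 and 14.7: ABR margin 3.5; mean change -2.5 with SD 8; baseline mean 3.5 (SD 7.8); post-infusion mean 1 (SD 1.8); negative binomial dispersion 2.2; n = 110; two-sided 0.05. The protocol gives neither the number dosed before a switch nor the true effect of a new dose. Both are assumed here: 20, 40, 60 or 90 subjects at the first dose with the planned change of -2.5, and 110 at a new dose with a true change of exactly +3.5, the null boundary.

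**The protocol's own figures.**
- Non-inferiority: effect size (3.5 + 2.5)/8 = 0.75. With n = 110, power is above 99.99% (stated: at least 95%).
- Superiority: 2.5/8 = 0.3125. With n = 110, power is 90.1% (stated: about 90%).

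**SD at the new dose.** SD 8 comes from √(7.8² + 1.8²) = 8.0. It therefore applies only where the post-infusion mean is 1, since √(1 + 2.2 × 1²) = 1.8. A change of +3.5 means a post-infusion mean of 7, with SD √(7 + 2.2 × 7²) = √114.8 = 10.7. The SD of change is then √(7.8² + 114.8) = 13.3. The baseline SD of 7.8 is reproduced by doubling a half-year count with mean 1.75 and dispersion 4.4: √[4 × (1.75 + 4.4 × 1.75²)] = 7.8.

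**Pooled mean and variance.** With w = n₁/(n₁ + 110):
- mean = w(-2.5) + (1 - w)(3.5)
- variance = w·8² + (1 - w)·s² + w(1 - w)·6², where s is the SD at the new dose.

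For n₁ = 20, w = 20/130 = 0.154 and the mean is 2.58, which is 0.92 below the margin. With s = 13.3, the pooled SD is 12.8 and the standard error 12.8/√130 = 1.12. The t-test then rejects in about 13% of trials by this approximation; simulation gives 14%.

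**Simulated probability of declaring non-inferiority** (repeat runs differ by about one percentage point):

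| First dose + new dose | True pooled mean | Negative binomial counts matching the protocol's SDs | Normal, SD 8 for both doses |
|---|---|---|---|
| 20 + 110 | 2.58 | 14% | 24% |
| 40 + 110 | 1.90 | 36% | 64% |
| 60 + 110 | 1.38 | 64% | 91% |
| 90 + 110 | 0.80 | 90% | >99% |
| New dose alone | 3.50 | 3% | 2.5% |

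The negative binomial column is the better guide, because SD 8 is too small for a dose at the margin. The pooled mean stays above 0 in every row, so the superiority test is not inflated in these settings.

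**The reverse case** (SD 8 for both doses): 110 subjects at a new dose performing as planned, pooled with 20 from a stopped dose at +3.5, have superiority power of about 58%. Analysed alone they have 90.1%.

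**The case against.** The case against is substantial.

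- **No sentence orders pooling.** The refill to about 130, regardless of prior enrolment, looks like a self-standing cohort, and section 14.3 counts 110 subjects, not more. This is a fair reading of intent. It does not alter section 14.8, which is explicit and takes in anyone infused; after a switch, nothing says which subjects make up the 110.
- **The SAP or an amendment could settle it.** The SAP is not shown and may separate doses. Section 14.9 provides for amendments, and a switch would date several sections. But the protocol fixes the populations itself, section 9.1 already authorises the new enrolment, and no section shown requires section 14.8 to be revised when a switch occurs.
- **The scenario is severe.** It needs an effective dose to be stopped and replaced by one that doubles bleeding (3.5 to 7), under a DMC that sees bleeding data. It also takes the ABR test in isolation, although two tests come before it in the hierarchy. This stands: the figures show the mechanism and are not a forecast.

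Two stronger readings are tempting. A reader might infer that a failing dose would itself be declared non-inferior. The documents do not support that: the hypothesis names BMN 270, so a weak dose would be covered by the declaration without being tested by name. A reader might also infer that about 130 dosed in section 14.7 flatly contradicts a total near 260 under section 9.4.6. That is mostly a base case and its exception, since section 9.4.6 is conditional on a dose change. It needs a clarifying sentence.

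**Conclusion.** The point holds as a conditional one. If the dose is switched, sections 14.2, 14.3 and 14.8 as written pool the two doses, and the error rate for the dose carried forward is not controlled. With a new dose exactly at the margin, the chance of a non-inferiority declaration rises from about 3% to between 14% and 90%, depending on how many subjects were treated first.

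The size rests on the assumed split, the assumed true effects and the protocol's dispersion model. The higher figures under a common SD of 8 overstate it. Without a switch there is no effect at all, so this is a should-fix contingency rule and not a defect in the base design.

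**What to change.** - **Section 14.8:** define the confirmatory mITT set, for the primary and secondary endpoints, as HIV-negative subjects treated at the dose level carried to the final analysis (6E13 vg/kg if there is no switch). Summarise efficacy at any discontinued dose separately, and present safety by dose.
- **Sections 14.7 and 9.4.5:** state that about 130 is the number at that dose level, and reconcile this with sections 9.1 and 9.4.6.

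This takes a few sentences, changes nothing if the dose is never switched, and says nothing about which dose is right. The price after a switch is that subjects on the stopped dose leave the confirmatory test. The refill to about 130 that the protocol already allows offsets this.
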